13.2 COLLECTION OF COMPLICATIONS

The products used in this study are well established and registered since many years. The manufacturers of the products used are responsible for safety monitoring for pharmacovigilance purposes according to regulations.

In this study, following complications will be collected up to 30 days post-surgery:

- Surgical (intraoperative) complications that receive a ICD-classification number
- Postoperative complications
- Postoperative morbidity related to surgery
- Occurrence of following diagnoses during 30 days after surgery: myocardial infarction, stroke, pulmonary embolism, pneumonia and renal failure

13.3 METHODS FOR ELICITING, RECORDING AND FOLLOW-UP OF COMPLICATIONS

For every complication as noted in section 13.2, only the start and end date will be recorded in the CRF for calculation of the duration of the event.

13.4 FOLLOW-UP OF COMPLICATIONS

The care of the patients is made according to each site's normal clinical practice and this includes the need of follow-up of any complications. There is no study specific procedure. The complications noted in section 13.2 that occur within 30 days after surgery will be noted in CRF.

20 (31)

Date: 28 Oct 2016

13.5 LABORATORY ASSESSMENTS

No protocol specific laboratory requirements. Data about CRP, liver enzymes (ASAT and ALAT), Bilirubin, Albumin and Creatinine obtained in normal clinical practice pre- and postoperative will be collected in the CRF.

14 STATISTICS AND DATA MANAGEMENT

14.1 DATA MANAGEMENT

UCR will be responsible for the Data Management of the clinical database and will write a study specific Data Management Plan (DMP) where further details will be specified.

An electronic CRF will be used in this study which also will serve as the clinical database for the study. UCR will be responsible for set-up, support and management of this electronic CRF. All demographic, anaesthesia related and surgical related data will be collected in this database.

This system will also include handling of queries to resolve any inconsistencies detected by the quality control procedures.

Tumor-specific variables including data about survival will not be part of this database but will be transferred from the quality registries used within oncology for the Swedish study population. These quality registries are routinely used within oncology as part of the quality assurance of the care of these patients (the INCA-platform is used). The registries are handled by six Regional Cancer Centers (RCC). The RCC registers includes a quality register for breast cancer, which was started in 1992 but also registers for colon cancer and rectal cancer which was started in 1995 and in 1997 respectively. These registers contain information on mode of detection, histopathology, and stage of cancer at diagnosis, other prognostic markers and complementary treatment given. Hence, complete oncologic- and outcome data will be available for all types of cancer included in the study within the defined period of time. Data on type and stage of the cancer, as well as different prognostic markers recorded in the oncologic registers will be extracted, as well as data on recurrences of disease, vital status and date and cause of death.

In order to be able to link the information in these databases, the patient's full personal identification number will be collected and noted for the Swedish and Polish study population. No personal identification number will be captured for the patients enrolled at the sites in other participating countries. The personal identification number will be deleted after data cleaning and merge of the databases, to ensure anonymity for each person. All analysis made will be on the whole population when the personal identification has been removed.

14.1.1 DATA VALIDATION

CRF data will be subject to both logical computerized checks and manual validation checks against listings in accordance with the study specific DMP. All inconsistencies

Clinical Study Protocol CAN version FINAL 2.0

Date: 28 Oct 2016 21 (31)

detected during these procedures will be resolved through queries, being issued to the monitor or investigational site personnel. The complete procedure will be described in the DMP.

14.1.2 DATABASE CLOSURE

When all patients have been completed (i.e. completion of follow-up 365 days post surgery), all data have been entered into the database, and all queries solved, the Database Closure procedures will start. Decisions will be made how to classify patients into analysis populations, and how to handle protocol violations and deviating or missing data. All decisions will be dated and documented in a Database Closure document. After that the database will be locked. Any changes in the database thereafter will be documented.

14.2 STATISTICAL ANALYSIS

The clinical database will be transferred to the Sponsor by UCR. Tumour-specific data will be transferred to the Sponsor from the RCC quality registers for the Swedish study population. For other countries, there will be local procedures to capture this data and to have the information transferred to the Sponsor. Sponsor will then be responsible for linking these databases and will also do the statistical analysis.

Based on the experience from study start, the breast cancer cohort has higher recruitment-rate than the colo- and rectal-cancer cohorts. Accordingly, recruitment of breast cancer patients will be completed earlier. Due to this, the analysis of the breast cancer cohort will be made earlier than the other two cohorts. Based on the outcome of this analysis, decision will be taken about further recruitment in the study.

In the present study all endpoints will be evaluated by descriptive methods. All variables will be presented as aggregated data. Categorical variables will be summarised in frequency tables (presenting frequencies and proportions) by type of anaesthesia. The quantitative variables will be summarised by number of observations (n), mean, standard deviation (SD), median, minimum (min) and maximum (max) by anaesthesia. If applicable, separate summaries will be presented for patients receiving one, two or more anaesthesia, as well as pooled summaries. Graphical methods may be used wherever it is regarded as appropriate.

Overall survival (OS) and time to progress (TTP) will be presented as Kaplan-Meier curves together with median survival time and time to progression, respectively.

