7 STUDY OBJECTIVES

We hypothesise that one- and five-year survival after radical breast-, or colorectal cancer surgery in general anaesthesia is 5%-units statistically significant higher in patients given the intravenously administered hypnotic propofol than in patients given the inhalational hypnotic sevoflurane.

The hypothesis is based on:

- 1) The knowledge about the opposite effects on the immune system from the two different forms of anaesthesia and from their different genotoxic potentials.
- 2) The well-established associations between the state of the immune system and cancer growth, and DNA damage and cancer development, with potential influences on survival.

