7.1 PRIMARY OBJECTIVE

The primary objective is to evaluate whether the one- and five-year survival after radical breast-, or colorectal cancer surgery in general anaesthesia is significantly higher in patients given the intravenously administered hypnotic propofol than in patients given the inhalational hypnotic sevoflurane.

The difference is seen as significantly higher and clinically relevant if the absolute difference in five-year-survival is minimum 5%-units.

8 **ENDPOINTS**

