8.2 PRIMARY ENDPOINT

The primary endpoint will be a comparison of overall survival using time to event (i.e. death) analysis. Time for death will be collected from the quality registries used within oncology for the Swedish study population. For other countries, there will be local procedures to capture this data.

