14.3 DETERMINATION OF SAMPLE SIZE

A clinically relevant absolute difference in five-year-survival would be 5%-units. Based on data from our retrospective study, we will have 80% power to detect a difference of 5%-units with a *P*-value of <0.05 if including 7,378 patients (see table below). By adding 8.4% more patients to the inclusion of 8,000 patients, we will have a reasonable safety margin for loss of patients or technical errors.

In-text table 14-1– tumor specific sample size calculation:

80% power and 5% significance demands for

Breast cancer with an expected 5-year survival of 87% vs 82% a number of:
Colon cancer with an expected 5-year survival of 60% vs 55% a number of:
Rectal cancer with an expected 5-year survival of 70% vs 65% a number of:
2 728 pts
Margin for loss of patients or technical errors

Total

8 000 pts

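### Section 14.2 and the synopsis make every endpoint descriptive, which contradicts the significance hypothesis and excludes the log-rank test the trial was sized for

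*Protocol*

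**What the plan says.** Four parts of the protocol describe a confirmatory trial.

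- Section 7 hypothesises that one- and five-year survival "is 5%-units statistically significant higher in patients given the intravenously administered hypnotic propofol than in patients given the inhalational hypnotic sevoflurane".
- Section 7.1 makes the primary objective whether survival "is significantly higher in patients given the intravenously administered hypnotic propofol than in patients given the inhalational hypnotic sevoflurane", and adds a decision rule: "The difference is seen as significantly higher and clinically relevant if the absolute difference in five-year-survival is minimum 5%-units".
- Section 8.2 says: "The primary endpoint will be a comparison of overall survival using time to event (i.e. death) analysis".
- Section 14.3 gives the size: "80% power to detect a difference of 5%-units with a *P*-value of <0.05 if including 7,378 patients". The accompanying table is built by tumour type.

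Section 14.2, with the same text in the synopsis, describes a descriptive one: "In the present study all endpoints will be evaluated by descriptive methods". It lists frequency tables and summary statistics, and for survival it says: "Overall survival (OS) and time to progress (TTP) will be presented as Kaplan-Meier curves together with median survival time and time to progression, respectively". The analysis text names no test, hazard ratio or confidence interval. Section 14.2 also has the breast cohort analysed first, with its outcome informing the decision on further recruitment.

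**The concern.** A protocol may leave the choice of test to a statistical analysis plan, and silence here would be no fault. Section 14.2 is not silent. It gives a rule for all endpoints, and overall survival is the primary one. A plan that follows 14.2 cannot answer 7.1, and a plan that adds a test departs from 14.2. The protocol text itself has to change.

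Two things are at stake. The primary objective asks about significance, and the analysis section contains no method that can establish it. The breast cohort result is also meant to guide further recruitment, yet the protocol ties that decision to no inferential criterion.

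**Working it through.** **1. Reproduce the sample size.** Inputs from section 14.3: five-year survival 87% vs 82% (breast), 60% vs 55% (colon), 70% vs 65% (rectal); power 80%; P<0.05. Allocation is 1:1 (section 11.5). Sidedness is not stated, so two-sided is assumed and then checked by whether the figures reproduce.

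Freedman's log-rank formula:
- HR = ln(S_propofol) / ln(S_sevoflurane)
- events = (1.960 + 0.842)² × [(1 + HR)/(1 − HR)]², with (1.960 + 0.842)² = 7.849
- N = events / (1 − mean five-year survival), rounded up per arm

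| Cohort | HR | Events | 1 − mean survival | N before rounding | N |
|---|---|---|---|---|---|
| Breast | 0.1393/0.1985 = 0.702 | 255.5 | 0.155 | 1,648.5 | 1,650 |
| Colon | 0.5108/0.5978 = 0.854 | 1,274.2 | 0.425 | 2,998.2 | 3,000 |
| Rectal | 0.3567/0.4308 = 0.828 | 886.2 | 0.325 | 2,726.8 | 2,728 |

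Sum: 1,650 + 3,000 + 2,728 = 7,378, exactly as stated. The rectal figure also matches exactly. The margin matches too: 8,000/7,378 = 1.084, the stated 8.4%.

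The alternatives fit less well. Two-proportion calculations give 7,466 (pooled variance: 1,644 + 3,068 + 2,754), 7,448 (unpooled) and 7,704 (continuity-corrected).

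**2. Can the 5-point rule in 7.1 serve as the test?** Take a two-sided 5% two-proportion comparison at five years, with the pooled standard error at the planned cohort sizes. The smallest significant observed difference is 1.96 × √(2p(1 − p)/n), where p is mean survival and n the number per arm:
- Breast: 1.96 × √(2 × 0.845 × 0.155/825) = 0.035
- Colon: 1.96 × √(2 × 0.575 × 0.425/1,500) = 0.035
- Rectal: 1.96 × √(2 × 0.675 × 0.325/1,364) = 0.035

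Significance is reached at about 3.5 points in each cohort, so the 5-point rule and a 5% test are different criteria. If the true difference is exactly 5 points, an unbiased and roughly symmetric estimate is 5 points or more with probability about 0.5. Used as the decision rule, the threshold would give about 50% power, not 80%.

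**3. Can the medians serve?** Expected five-year survival is 55% or more in every arm, so on the protocol's own figures every median lies beyond five years. The medians say little about the five-year contrast in the objective.

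**The case against.** The strongest reply is that a test was plainly intended. Section 8.2 calls for a time-to-event comparison, section 14.3 gives a P-value and power, and an analysis plan may name the test before any outcome data are linked. The intention is clear, and step 1 confirms it. That makes this a contradiction to reconcile. It does not remove the contradiction, because 14.2 speaks of all endpoints.

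A second reply is that the log-rank reading is an inference. The pooled two-proportion total of 7,466 is within 1.2% of 7,378, and the breast and colon entries are not legible in the copy of the table available. This is fair, but only the Freedman calculation matches both the total and the rectal entry exactly. Either reading leaves the trial sized for a significance test within each cohort.

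Some stronger conclusions are tempting but not supported:
- A reader might infer that the trial must end with two curves and no comparison. Section 8.2 prescribes a comparison, and 14.2 does not say that the curves and medians are the only output for survival.
- A reader might infer that any test would be chosen after the data are visible. That cannot be known, since an analysis plan may exist.
- A reader might infer that the collected prognostic variables will go unused. The protocol does not say so, and covariate adjustment is commonly left to the analysis plan.
- A reader might want one pooled log-rank test stratified by tumour type as the primary analysis. At the protocol's rates that test would rest on about 1,650 × 0.155 + 3,000 × 0.425 + 2,728 × 0.325 ≈ 2,417 events and have about 99.7% power. It is not the 80% tumour-specific test of 14.3, and it does not cover the breast-first analysis.

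**Conclusion.** The point holds as a direct contradiction within the protocol. Section 14.2 and the synopsis rule out inference for every endpoint, while sections 7, 7.1, 8.2 and 14.3 require it for overall survival. The omitted test is the one that fixed the size of the trial: 7,378 patients, reproduced to the patient as three two-sided 5% log-rank calculations. The 5-point threshold is no substitute, since it sits about 1.5 points above the significance boundary and would have about 50% power at the design difference.

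The conclusion rests on the stated survival rates and on two-sided testing, which the exact reproduction supports. The 3.5-point boundary uses a five-year two-proportion approximation without censoring. The contradiction itself depends on no calculation. It must be corrected, because the primary objective has no analysis in section 14.2 that can answer it.

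**What to change.** In section 14.2 and the synopsis, limit the descriptive sentence to non-primary variables and add:

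> Primary analysis: overall survival compared between arms within each tumour cohort (breast, colon, rectal) by a two-sided log-rank test at 5%, with hazard ratio and 95% CI and the Kaplan-Meier difference in 5-year survival with 95% CI.

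This matches the tumour-specific sizing in 14.3 and gives the earlier breast cohort analysis a stated method. Any pooled stratified or covariate-adjusted analysis should be labelled supportive. Section 7.1 should present the 5 points as the margin of clinical relevance, distinct from statistical significance.

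The cost is an amendment of wording. It needs no new data, no change in sample size and no change to the analysis population in 14.2.1.

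### Median survival is the only number named beside the overall-survival curves, yet on the protocol's own rates no arm reaches its median within five years, so it cannot express the five-year objective

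*Protocol*

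**What the plan says.** Section 14.2 and the statistical-methods part of the synopsis carry the same sentence: "Overall survival (OS) and time to progress (TTP) will be presented as Kaplan-Meier curves together with median survival time and time to progression, respectively". For overall survival, the primary endpoint in section 8.2, the median is the only number tied to the curves.

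The objective (synopsis and section 7.1) concerns survival at one and at five years. It makes a gap of at least 5 percentage points at five years the test of clinical relevance. Section 14.3 repeats this, "A clinically relevant absolute difference in five-year-survival would be 5%-units", and builds the sample size on three pairs of five-year rates. The lowest pair is for colon: "Colon cancer with an expected 5-year survival of 60% vs 55% a number of". The pair for rectal is 70% against 65%, and the pair for breast is 87% against 82%.

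Section 14.2 also says that the breast cohort will be analysed before the other two, and that the result will guide the decision on further recruitment.

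**The concern.** A median survival time exists on a Kaplan-Meier curve only once the curve has fallen to 50%. Where survival stays well above that level, the entry in the table reads *not reached* for both arms and does not separate them. Here the protocol fixes such a summary while stating rates that all lie above 50% at its own horizon.

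This goes beyond an omitted detail. The summary chosen does not measure what the objective asks about, and the estimates that would measure it are not named beside the curves. The mismatch is greatest for breast cancer, the cohort read first and used to decide whether recruitment goes on.

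**Working it through.** **Inputs.** Five-year survival by cohort, 80% power, 5% significance and the total of 7,378 come from section 14.3. The 1:1 allocation comes from section 11.5 and the calendar dates from section 6.2. The table does not label the arms. The higher rate is taken as propofol, in line with the hypothesis in section 7.

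**Step 1: reproduce the plan's figure, to confirm that the rates are read correctly.** Freedman's log-rank formula, two-sided 5%:

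- HR = ln(S1)/ln(S2)
- events = (1.960 + 0.842)² × ((1 + HR)/(1 − HR))²
- N = events/(1 − mean five-year survival), rounded up to an even number

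| Cohort | HR | Events | Divisor | N |
|---|---|---|---|---|
| Breast | 0.7017 | 255.5 | 0.155 | 1,648.5 → 1,650 |
| Colon | 0.8545 | 1,274.2 | 0.425 | 2,998.2 → 3,000 |
| Rectal | 0.8280 | 886.2 | 0.325 | 2,726.8 → 2,728 |

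The sum is 1,650 + 3,000 + 2,728 = 7,378, the protocol's total. The rectal figure matches the one printed in the table.

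**Step 2: is any median within five years?** The lowest of the six rates is 55% (colon, lower arm). Survival above 50% at year 5 places the median beyond year 5. This needs no assumption about the shape of the curve.

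Chance does not change it. With 1,500 patients in that arm and complete follow-up, SE = √(0.55 × 0.45/1,500) = 0.0128. The distance to 50% is 0.05/0.0128 = 3.9 standard errors, a probability of about 0.00005.

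**Step 3: how far out do the medians lie?** Constant hazard: median = 5 × ln(0.5)/ln(S5). As a range, Weibull shapes 0.7 and 1.3: median = 5 × (ln(0.5)/ln(S5))^(1/shape).

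| Cohort, S5 | Constant hazard | Shape 1.3 | Shape 0.7 |
|---|---|---|---|
| Breast 87% | 24.9 y | 17.2 y | 49.5 y |
| Breast 82% | 17.5 y | 13.1 y | 29.9 y |
| Colon 60% | 6.8 y | 6.3 y | 7.7 y |
| Colon 55% | 5.8 y | 5.6 y | 6.2 y |
| Rectal 70% | 9.7 y | 8.3 y | 12.9 y |
| Rectal 65% | 8.0 y | 7.2 y | 9.9 y |

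**Step 4: how long could anyone be followed?** Section 6.2 has the first patient in from the third quarter of 2013 and five-year compilation from the second quarter of 2023 to the second quarter of 2025. For the very first patient that is 2023.25 − 2013.5 = 9.75 years up to 2025.5 − 2013.5 = 12.0 years. Later enrollees have less.

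- Breast: even 13.1 years exceeds 12.0, so the median is not reached in either arm.
- Colon: 5.6 to 7.7 years falls inside the span and could be reached if follow-up past five years is used.
- Rectal: 7.2 to 12.9 years might be reached, but only from the earliest enrollees.

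**Step 5: is the quantity in the objective estimable?** SE of the five-year difference, complete follow-up, half of each N per arm:

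- Breast: √((0.87 × 0.13 + 0.82 × 0.18)/825) = 1.78 points
- Colon: √((0.60 × 0.40 + 0.55 × 0.45)/1,500) = 1.80 points
- Rectal: √((0.70 × 0.30 + 0.65 × 0.35)/1,364) = 1.79 points

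A 95% interval is therefore about ±3.5 points (1.96 × 1.8) around a target difference of 5.

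**The case against.** Four points can be made for the plan.

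1. *Follow-up is not capped at five years.* This stands. A reader might infer that no median can be estimated in any cohort, but the protocol states no censoring at five years and its dates leave room for colon and perhaps rectal medians. The secure statement is that no median is expected within five years and that breast is not reached at all. A colon or rectal median driven by early enrollees still would not answer a five-year question.

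2. *The one- and five-year results will be available anyway.* This stands in part. A reader might infer that the five-year difference will never be produced. However, the synopsis lists survival at both times among its criteria for evaluation, the curves contain both values, and section 14.2 plans proportions by type of anaesthesia. But reading two curves gives no interval for their difference, and a crude proportion does not handle censoring, for which section 14.3 sets aside an 8.4% margin.

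3. *The sentence concerns presentation, and effect measures belong in an analysis plan.* This is fair as far as the missing hazard ratio and intervals go: their absence alone would be no finding. The point rests on what the protocol does state, twice: a summary that does not fit its own rates and criterion.

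4. *A median that is not reached does no harm.* Correct: it biases nothing, invalidates no test and loses no data. That limits the weight of the point.

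A reader might also infer that the Kaplan-Meier presentation of time to progression overstates recurrence by censoring deaths. The documents do not support this. They state no censoring rule for that endpoint and give no rates from which to judge it.

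**Conclusion.** The point holds, limited to overall survival and to the fit between the named summary and the objective. All six assumed five-year rates are 55% or higher, so no arm is expected to reach its median within five years. That conclusion rests only on the protocol's rates.

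The breast median (17.5 to 24.9 years under a constant hazard) lies beyond the longest follow-up the timetable allows, about 12 years. This second conclusion assumes a hazard that does not rise steeply: it holds at Weibull shape 1.3, where the lower breast arm gives 13.1 years. Whether colon and rectal medians are reached depends on accrual and on the follow-up used, which the protocol does not settle.

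The consequence is a named summary that cannot show whether the 5-point criterion is met and that will be empty for the cohort analysed first. It is a defect of specification that should be corrected, and does not threaten the validity of the trial.

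**What to change.** In section 14.2 and in the synopsis, replace the overall-survival part of the sentence with wording such as: *Overall survival will be shown as Kaplan-Meier curves by arm and cohort. The main summaries are the Kaplan-Meier estimates at 1 and 5 years, the between-arm difference at 5 years with 95% CI, and the hazard ratio with 95% CI as the time-to-event effect measure. Median survival is reported only where it is reached.* The wording on time to progression can stay as it is.

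The change should be in place before the breast cohort is analysed, because that result feeds the recruitment decision.

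The cost is one sentence in two places, documented as an amendment under section 21.1, and slight extra analysis of data already planned for collection. If the analysis plan already names these estimates, only the protocol text needs aligning.
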